3) Determine the effect of maternal anxiety on the association between placental molecular changes on pregnancy and birth and infant outcomes.

Hypotheses:

1a) Increased values for measures of prenatal maternal anxiety, stress, and depression will be associated with increased placental pathology.

2a) Increased values for measures of prenatal maternal anxiety, stress, and depression will be associated with increased Th1 response in respect to both Th2 and Th17 immunological response.

1b & 2b) Increased values for measures of prenatal maternal anxiety, stress, and depression will correspond with both increased oxidative stress and general stress hormones.

9.4 Study Design:

Describe study design in one to two sentences (e.g., prospective, use of existing records/data /specimens, observational, cross-sectional, interventional, randomized, placebo-controlled, cohort, etc.). Specify the phase – Phase I, II, III, or IV – for FDA-regulated investigational drug research

The study is a repeated measures, longitudinal design in which Active duty and DoD beneficiary pregnant women, 18 years of age and older, that are currently being recruited and consented for the Mentors Offering Maternal Support (M-O-M-S) research program at the Brooke Army Medical Center (BAMC). They will also be invited to participate in the placental study, as well as pregnant women entering prenatal care in the first trimester, who are not in the M-O-M-S program. Women choosing not to participate in the M-O-M-S study can elect to participate only in the placental study. Psychosocial measures of prenatal anxiety, depression and resilience will be collected at study entry and 12, 16, 24, and 32 weeks gestation. Placentas, of women consented to this study will be obtained following delivery.

No inducements, monetary or otherwise, will be offered to terminate a pregnancy [45 CFR 46.204 (h)]. Individuals engaged in the research will have no part in any decisions as to the timing, method, or procedures used to terminate a pregnancy [45 CFR 46.204(i)]. Individuals engaged in the research will have no part in determining the viability of a neonate [45 CFR 46.204(j)].

9.5 Target Population:

Describe the population to whom the study findings will be generalized

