11.0 Statistical/Data Analysis Plan

11.1 Statistical Considerations:

List the statistical methods to be used to address the primary and secondary objectives, specific aims, and/or research hypotheses. Explain how missing data and outliers will be handled in the analysis. The analysis plan should be consistent with the study objectives. Include any sub-group analyses (e.g., gender or age group). Specify statistical methods and variables for each analysis. Describe how confounding variables will be controlled in the data analysis

For characterization and identification of specific immunological, inflammatory, and hormone biomarkers changes, placental tissue biopsies taken from the same locations as the tissue for the paraffin blocks, will be flash-frozen in liquid nitrogen prior to being sent (by courier) to the 59th MDW Center of Advanced Molecular Detection (CAMD) at JBSA-Lackland. Once received, each biopsy will be homogenized and divided into two groups for analysis: (1) RT-PCR for RNA expression; (2) Multiplexed panel for protein expression. Response groups will be divided into: (1) Th1, (2) Th2, (3) Hormonal, and (4) Oxidative Stress, and some of their specific factors are summarized in **Table 1**.

Table 1: Select Immunological, Hormonal, and Oxidative Stress Factor for Analysis.

Th1	Th2	Th17 (Treg)	Oxidative Stress	Stress Hormone
IFN-γ	IL-3	IL-17	Hydrogen Peroxide	Prostaglandin E2
TNF-β	IL-4	IL-23	Nitric Oxide Synthase Family	Cortisol
TNF-α	IL-5	TGF-β	S-glutathionylation	CRH (HPA Axis)
IL-12p70	IL-10		C-reactive Protein	ATCH
IL-18	IL-13			DHEA
IL-1β	LIF			
IL-6				
IL-2				
MIP-1α				

Specifically, analysis will explore the physiological correlations between the biomarker groups as a response to psychosocial factors and in relation to histopathological analysis. The psychosocial measures obtained at various timepoints in first, second, and third trimester are presented in Table 2.

Table 2.

Variable	Measurement	Collection Timepoints

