Statistical Analysis System (SAS) version 9.4 will be used for all analyses. Descriptive statistics (mean, sd, median for each continuous variable and proportions for each discrete variable) will be used to describe the sample. Linear or generalized linear mixed models will be developed for all variables, prenatal anxiety, self-esteem, family adaptability/cohesion, prenatal depression and perceived support, as well as the protein and RNA values, in order to examine their association with placental metrics across pregnancy. The linear (mixed) model will be used for all normally distributed continuous data. In the case of skewed continuous outcome data, the generalized linear (mixed) model with gamma distribution and log-link will be chosen. For binary or dichotomized outcomes, a mixed model logistic regression will be chosen. Measurement times (dates of data collection by gestational age), will be included in the models as predictors when available with and without adjusting for the participant's age, employment status, prior deliveries, marital/partner status, education, deployment of partner during pregnancy, military branch of service of participant or partner, ethnicity, military rank of participant or partner and MOPS group. In the case of dual military couples, the rank and service of the active duty woman will be used. The final models will be determined with backward elimination procedure. Timing of data collection (weeks gestation), may also be chosen as a random effect within the model. Additionally, each prenatal variable (prenatal anxiety, self-esteem, depression, family adaptability/cohesion and resilience) will be longitudinally regressed on measurement time to obtain the slope through best linear unbiased predictor (BLUP). The resulted individual slopes will be used to determine any significant effects for prenatal psychosocial scores to pregnancy complications, birth and infant outcomes, and to the physiologic data (both placental scores and biomarker data).

To examine if anxiety mediates the relationship between biomarkers and birth outcomes, we will develop a Baron and Kenny (1986) mediation model assess the relationships as in Bauer and Preacher (2006). We will conduct three mixed regression models adjusted for all appropriate covariates:

1. Regress birth outcome on biomarker.
2. Regress birth outcome on biomarker and anxiety.
3. Regress anxiety on biomarker.

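### Section 11.6 carries psychosocial scores to biomarkers and outcomes as slopes, while hypotheses 2a and 1b/2b concern how high the scores are; the level should be entered as well

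*Protocol*

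**What the plan says.** Section 9.3 states its numbered hypotheses in terms of higher values of prenatal anxiety, stress and depression. Under 2a such values "will be associated with increased Th1 response in respect to both Th2 and Th17 immunological response". Under 1b and 2b they "will correspond with both increased oxidative stress and general stress hormones".

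Section 11.6 uses the psychosocial scores in three ways:

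- **Mixed models of the scores themselves**, and of the protein and RNA values, "in order to examine their association with placental metrics across pregnancy".
- **Individual slopes:** "each prenatal variable (prenatal anxiety, self-esteem, depression, family adaptability/cohesion and resilience) will be longitudinally regressed on measurement time to obtain the slope", by best linear unbiased prediction (BLUP). On how these are used, the plan says: "The resulted individual slopes will be used to determine any significant effects for prenatal psychosocial scores to pregnancy complications, birth and infant outcomes". It then names one more target for the slopes: "and to the physiologic data (both placental scores and biomarker data". No intercept, mean or other level is named as carried forward from this model.
- **Mediation models for anxiety**, for example "Regress birth outcome on biomarker and anxiety", without saying whether anxiety enters as a level or a slope.

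Section 11.1 adds that "analysis will explore the physiological correlations between the biomarker groups as a response to psychosocial factors", but names no summary of the psychosocial scores.

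**The concern.** A slope measures change over pregnancy; the biomarker hypotheses are about height. Table 2 defines the constructs by height too: higher PSEQ scores mean more anxiety, and an EPDS score of 12 or more is associated with prenatal depression.

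If section 11.6 is followed as written, hypotheses 2a and 1b/2b are tested for depression through change alone. A real relation between depression level and a biomarker could be missed. It could also appear with the wrong sign if women who score high tend to fall over pregnancy. Either result could be reported as the answer to a hypothesis it did not test.

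For complications and birth and infant outcomes the point is weaker. No numbered hypothesis covers them, and change is a legitimate exposure there. The level is simply left out for every score except anxiety.

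**Working it through.** **1. What each planned analysis covers**

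| Analysis | Score summary | Covers 2a and 1b/2b? |
|---|---|---|
| Mixed models, section 11.6 | Repeated scores | No. The target is placental metrics (hypothesis 1a). Protein and RNA values are listed beside the scores as variables set against those metrics, and biomarker data are later named apart from placental scores. |
| Individual slopes, section 11.6 | BLUP slope | Reaches the biomarkers, but as change |
| Mediation models, section 11.6 | Anxiety, form not stated | Not for depression; in model 3 anxiety is the outcome |
| Correlations, section 11.1 | Not stated | Undetermined |

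For depression, the slope is the only summary clearly named for the biomarker link.

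**2. Is there a plan figure to reproduce?** Not on this point. Section 11.5 gives 1200 deliveries, 80% power and a significance level of .05, but no effect size. The argument does not rest on that figure.

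**3. Illustration**

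From the protocol: n = 1200; visits at entry, 12, 16, 24 and 32 weeks. Assumed: entry at week 9, time centred at 20.5 weeks, level SD 1, slope SD 0.5 per 20 weeks (0.025 per week), residual SD 0.6.

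With X the matrix of intercept and centred time, G the covariance matrix of level and slope, and V = XGX' + 0.6²I, the BLUPs are GX'V⁻¹(score − mean). The outcome is regressed on the BLUP slope alone, or on BLUP level and slope together. There are 2000 replicates per scenario, with two-sided 5% tests.

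*Outcome driven by level* (correlation 0.10 / 0.15 with level):

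| Level–slope correlation | Slope alone rejects | Level in joint model rejects |
|---|---|---|
| 0 | 4% / 6% | 92% / 100% |
| +0.3 | 29% / 56% | 86% / 99% |
| −0.3 | 37% / 70%, at least 99.9% of these with reversed sign | 82% / 99% |

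*Analytic check of one cell* (0.10, level–slope correlation −0.3). The covariance matrix of the BLUPs is C = GX'V⁻¹XG. The correlation of outcome with BLUP slope is 0.10 × C₁₂/√C₂₂ = 0.10 × (−0.481) = −0.0481. The non-centrality is −0.0481 × √1198 / √(1 − 0.0481²) = −1.67. Power is Φ(1.67 − 1.96) = Φ(−0.29), about 0.38, all in the wrong tail. This agrees with the simulated 37%.

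*Outcome driven by slope* (correlation 0.10 / 0.15 with slope): slope alone 54–61% / 90–93%; slope in the joint model 49–54% / 84–90%; joint level 4–5%, which is chance. Adding the level costs the slope test nothing at correlation 0, and 6 to 12 points at ±0.3.

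*Reliability*, var(BLUP)/var(true effect), with level and slope uncorrelated:

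| | 5 visits | Visits to 24 weeks |
|---|---|---|
| Slope | 0.38 | 0.19 |
| Slope, slope SD varied 0.3–0.8 | 0.18–0.61 | 0.08–0.38 |
| Level | 0.93 | 0.91 |

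**4. Other variance components.** A separate run used centring at week 20, slope SD 0.03 per week, residual SD 0.7, 1000 replicates and a level effect of 0.1 SD.

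| Level–slope correlation | Slope alone | Joint level |
|---|---|---|
| 0 | 6% | 91% |
| −0.3 / +0.3 | 36% / 26% | 82% / 85% |
| −0.5 / +0.5 | 68% / 62% | 62% / 66% |

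The two-degree-of-freedom test of level and slope together stayed at 83–85% throughout. In these level-driven runs the slope term in the joint model rejected in about 5%, so it no longer carries the level effect.

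**The case against.** - **Slopes are an addition.** The mixed models of the scores come first, and placental metrics is not defined. The biomarkers are measured in placental tissue, so the term might include them. However, section 11.6 lists protein and RNA values alongside the scores rather than among the metrics, and later separates placental scores from biomarker data. The narrower reading is the better supported one.
- **Anxiety and stress have another route.** One instrument, the PSEQ, measures both, and the mediation models use anxiety without calling it a slope. This stands as a limit: the firm gap is depression against biomarkers.
- **Higher values could mean rising values** in a repeated-measures design. This is possible, but less natural given how Table 2 describes the scales.
- **This is detail for an analysis plan.** The protocol is not silent, though. It names a summary, and an analysis plan that follows it inherits the mismatch.
- **The sizes follow from assumptions.** This stands. Chance-level rejection at zero correlation follows by construction, and the reversed sign needs a negative correlation for which the protocol gives no evidence. Centring matters too. If level and slope were uncorrelated at week 9, the correlation at week 20.5 would be (11.5 × 0.025)/√(1 + 0.2875²) = 0.28, close to the +0.3 row.
- **More tests.** Table 1 lists 27 biomarker entries, so a level test beside each slope test doubles the count. This is a real cost, but minor while purposes 1 and 2 are worded as exploratory.

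**Conclusion.** The point holds and should be acted on. Section 11.6 fixes an exposure that does not answer hypotheses 2a and 1b/2b as worded, most clearly for depression. For birth outcomes the claim is only that the analysis is incomplete. Hypothesis 1a already has a score-based analysis.

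The qualitative result does not depend on the assumed variances: a slope unrelated to level carries essentially no information about a level effect, whatever the sample size. The percentages do depend on the assumed variance components, entry week, centring and effect sizes, and should be read as illustration. The slope remains a legitimate second exposure and fits the rationale for repeated measures.

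**What to change.** In section 11.6:

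1. From the same mixed model, with gestational time centred at a stated week near 20, output the BLUP level as well as the BLUP slope.
2. Enter both together in the models for biomarkers, placental scores, complications, and birth and infant outcomes.
3. State that the level coefficient tests the hypotheses on higher values (2a, 1b/2b, and 1a where slopes are used), and that the slope coefficient answers the question on change.
4. Optionally, as a sensitivity check for preterm birth, derive the exposure in all women from visits up to 24 weeks, since deliveries before 32 weeks necessarily lose the last visit. Slope reliability is low there (0.19 in the illustration), so read mainly the level.

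The cost is one further output from a model already planned, one more covariate per regression and an added set of tests, with no new data. In the illustration the slope test loses 0 to 12 points of power. If level and slope are strongly correlated (±0.5), the level coefficient itself falls to 62–66% power, so the joint two-degree-of-freedom test is worth reporting beside it.

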Prenatal maternal anxiety and depression have been implicated as possible risk factors for preterm birth (PTB) and other poor birth outcomes (Ding et al., 2014; Doktorchik et al., 2018; Reck et al., 2013). Preterm deliveries are considered to be one of the key indicators for national health and is the leading cause of neonatal death as well as the second most frequent cause of death in children aged < 5 years worldwide (WHO, 2012). Every year, approximately 15 million babies are born prematurely worldwide, which equates to 1 out of every 10 babies (WHO, 2012). In the U.S., the estimated annual cost of PTB is approximately 26 billion dollars (IOM, 2007), which includes maternal delivery costs, medical care for the infant up to age 5 years, early intervention, and disability-specific lifetime medical costs. In addition, PTB outcomes are closely related to low birthweights (LBW), which accounted for 22 million newborns worldwide in 2015. Following this report, the World Health Organization established new goals for 2025 to decrease low birthweight (LBW) by 30% and improve maternal health (WHO, 2014). Overall, etiology underlying maternal mental health and its relationship to PTB and LBW is poorly understood. Literature has theorized that stress-associated chronic inflammation and oxidative stress leads to changes that disrupts immunological homestasis that then triggers preterm labor. Concurrently, stress-associated cellular damage can result in an acute inflammatory response and significant cytokine upregulation (Tsiartias, 2012). Alternatively, the disruption of normal placental development can lead to alterations in placental vasculogenesis and angiogenesis as well as changes in hormone and enzyme activity results in placental insufficiency leading to impaired fetal growth and reduced birth weight (Parra-Saavedra et al., 2013).

Background and Review of Literature:

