Research efforts in the investigation of reproductive health, especially as it relates to mental health of active-duty servicewomen, female veterans, or wives of service members is limited (Ganzer, 2016). As operational conditions have intensified so has the stress and anxiety experienced by the active duty member and their spouses (Verdeli et al., 2011). As result of these stresses, many veterans are reported to have long-term mental health issues associated with their service. Mental health along with physical condition, socioeconomic status, and the availability of social support can significantly impact pregnancies. As operational stress and anxiety rise for active duty women coupled with lack of necessary social support increases the likelihood of pregnancy complications and poor birth outcomes (Dunkel-Schetter, 2011). To better elucidate the roles of mental health and social support on birth outcomes, it is important to the examine how these psychological factors are manifested physiologically. Although literature has shown that the biopsychosocial mechanisms PTB are driven by an inflammatory/immune response resulting from the activation of the hypothalamic-pituitary-adrenal (HPA) axis, there are limited understanding the mechanisms that leads to LBW. However, it is hypothesized that elevated proinflammatory cytokines and C-reactive proteins (Coussons-Read et al., 2007) that is seen in PTB might also play role in LBW. Conceivably, inflammatory/oxidative stress responses leading to alteration in cellular functions and placental development affects fetal nutrient transport, which ultimately results in lower birth weights. Prospective studies are, in which pregnant women are followed across pregnancy, with repeated measures of anxiety and symptoms of depression are needed to be compared to pathological placental changes and molecular biomarkers associated with poor birth outcomes.

9.3

Objectives/Specific Aims/Research Questions:

Describe the purpose and objective(s) of the study, specific aims, and/or research questions/hypotheses

Purpose of Study:

- 1). Explore the associations of prenatal maternal anxiety to placental histological findings
- 2). Explore the associations between prenatal maternal anxiety and the function of pro-inflammatory, anti-inflammatory, and immunoregulatory cells found in placental tissue.

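### The mediation model in 11.6 puts biomarker and anxiety in the reverse of the protocol's own causal order, and no planned model tests purpose 3 as worded

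*Protocol*

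**What the plan says.** Protocol 11.6 (Data Analysis Plan) introduces a Baron and Kenny mediation model "To examine if anxiety mediates the relationship between biomarkers and birth outcomes". It lists three regressions: birth outcome on biomarker; birth outcome on biomarker and anxiety; and "Regress anxiety on biomarker". The first two are to be logistic and the third linear or generalized linear. The question and the three models agree with each other: exposure is the biomarker, mediator is anxiety.

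The same section, just before this, plans individual psychosocial slopes as predictors: "The resulted individual slopes will be used to determine any significant effects for prenatal psychosocial scores to pregnancy complications, birth and infant outcomes", and of the placental and biomarker data as well.

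Purpose 3 in 9.3 reads "Determine the effect of maternal anxiety on the association between placental molecular changes on pregnancy and birth and infant outcomes".

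On timing, 9.4 states "Psychosocial measures of prenatal anxiety, depression and resilience will be collected at study entry and 12, 16, 24, and 32 weeks gestation". According to 10.1 the molecular data come from the placenta after delivery, and 14.6 says that no blood is drawn, so there is no earlier biomarker.

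**The concern.** The planned mediator is measured before the planned exposure, and the third model regresses a prenatal score on a post-delivery assay. The protocol's own reasoning runs the other way. Section 9.2 describes theory in which "stress-associated chronic inflammation and oxidative stress leads to changes that disrupts immunological homestasis that then triggers preterm labor", and suggests that "inflammatory/oxidative stress responses leading to alteration in cellular functions and placental development affects fetal nutrient transport, which ultimately results in lower birth weights". Section 11.1 treats the analysis as one of "the physiological correlations between the biomarker groups as a response to psychosocial factors".

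If that rationale is true, the planned model estimates the wrong path. It can miss a real stress-to-biomarker-to-outcome pathway, and it can label a confounder (anxiety driving both biomarker and outcome) as a mediator.

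Purpose 3 asks how anxiety affects an association. Read literally, that is effect modification, and it needs an anxiety-by-biomarker term that none of the three models contains. Purposes 1 and 2 are not affected, and the hypotheses in 9.3, worded as associations, are not contradicted.

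**Working it through.** **Inputs.** The documents give no figure for the mediation analysis, so there is none to reproduce. From the protocol: n = 1200 (11.2) and significance level 0.05 (11.5). Assumed: 10% outcome prevalence, standardised anxiety and biomarker, correlation r between them, and log-odds ratios b (biomarker, given anxiety) and c (anxiety, given biomarker).

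**What each order estimates.** With standardised variables, on the log-odds scale:

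- Planned order: slope of anxiety on biomarker × effect of anxiety with the biomarker held fixed = r × c.
- Order of the rationale: slope of biomarker on anxiety × effect of the biomarker with anxiety held fixed = r × b.

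The planned product uses c, the part of anxiety's effect that does not pass through the biomarker. This follows from the models as written and needs no simulation.

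**Simulation.** 2000 replicates per scenario, logistic outcome models, two-sided 0.05. The interval for the product was simulated from the normal distributions of the two path coefficients.

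*1. Anxiety acts only through the biomarker (c = 0).* The planned product is r × 0 = 0.

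| r, b | r × b | Planned, three steps | Re-ordered, three steps | Re-ordered, interval |
|---|---|---|---|---|
| 0.15, 0.30 | 0.045 | 3.8% | 7.9% | 86.7% |
| 0.20, 0.35 | 0.070 | 5.4% | 10.2% | 94.2% |
| 0.25, 0.40 | 0.100 | 5.6% | 17.3% | 98.0% |

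Re-ordering alone gains little because step 1 then tests anxiety's total effect, about r × b. Its standard error is roughly 1/√(1200 × 0.10 × 0.90) = 1/√108 = 0.096. The expected z-values are 0.045/0.096 = 0.47, 0.070/0.096 = 0.73 and 0.100/0.096 = 1.04, so step 1 has power of only about 8%, 11% and 18%, in line with the table.

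With r = 0.20 and b = 0.35 at 8% and 12% prevalence, the planned three steps give 4.8% and 5.4%, the re-ordered three steps 8.8% and 11.0%, and the two re-ordered path coefficients are both significant in 88.9% and 96.9%.

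*2. Biomarker inert, anxiety drives both (b = 0).* The true path through the biomarker is zero.

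| r, c | Planned product r × c | Planned steps 2 and 3 | Planned, three steps | Re-ordered, interval |
|---|---|---|---|---|
| 0.15, 0.30 | 0.045 | 86.4% | 5.9% | 4.8% |
| 0.20, 0.35 | 0.070 | 93.3% | 11.5% | 5.3% |
| 0.25, 0.40 | 0.100 | 97.8% | 17.2% | 4.6% |

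*3. Partial mediation (r = 0.20, b = 0.35).* For c = 0.1, 0.2, 0.3 the planned product is 0.20 × c = 0.02, 0.04, 0.06 (simulated 0.020, 0.040, 0.059), and all three planned steps are significant in 17.0%, 49.2% and 82.0%. The path through the biomarker is 0.20 × 0.35 = 0.07 throughout (simulated 0.070, 0.071, 0.070). The planned result tracks the direct effect, not the pathway.

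*4. Effect modification only (r = 0.20, b = 0.35, c = 0).* For an interaction log-odds ratio of 0.2, 0.3, 0.4, an interaction term is significant in 60.0%, 90.6% and 99.3%; the three planned steps in 6.0%, 15.1% and 18.4%.

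**Stronger assumed effects** (r = 0.4, log-odds ratio 0.5, 400 replicates). Under full mediation, all three steps are significant in 4% in the planned order and 57.5% re-ordered. With an inert biomarker, they are significant in 57% as planned and 6% re-ordered.

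**The case against.** Several points on the other side have force.

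- *Weight.* The study is observational, purpose 3 has no listed hypothesis, and the sample size does not rest on mediation. The slope analysis already estimates anxiety to biomarker and anxiety to outcome in the forward direction. This limits the damage to purpose 3, but it does not rescue that purpose: the slopes give separate links, with no indirect effect and no interaction.
- *Source of the gain.* Most of the rise to 87-98% comes from dropping the requirement that step 1 be significant, not from the order. That is right, and both changes are needed. In the planned order, though, the product is zero under full mediation whatever the decision rule.
- *False mediation.* The 86-98% uses steps 2 and 3 only. If all three steps are required, the rate is 6-17% under the main assumptions and 57% under the stronger ones. The size is assumption-driven, and the simulations use one anxiety value, one biomarker and no covariates.
- *Timing.* Tissue taken after delivery reflects processes during pregnancy, so the collection date alone does not prove order, and the re-ordered model also has a mediator sampled at delivery. This stands as a limitation to be stated. The stronger ground is the conflict with the protocol's rationale. That rationale is put tentatively, but it is the only direction the protocol argues for.
- *Wording of purpose 3.* It is loose, and mediation may have been meant. The cited multilevel paper mentions moderated mediation in its title, but the three listed models carry no moderation term. On either reading purpose 3 has no valid test: if mediation is meant the roles are reversed, and if modification is meant the term is absent.

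**Conclusion.** The concern holds and should be fixed before purpose 3 is analysed. The protocol does not leave this open for later; it states specific models that cannot answer one of its three purposes. If the protocol's rationale is true, the planned analysis detects the pathway at about chance level (4-6%). With partial mediation it can be significant without measuring that pathway. It has little sensitivity to the effect modification that purpose 3 describes (6-18%, against 60-99% for an interaction term). These percentages rest on the assumed prevalence, correlation and log-odds ratios. The reversal of roles and the absent interaction term rest on the text alone.

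**What to change.** In 11.6, replace the three regressions with: (1) birth outcome on anxiety; (2) birth outcome on anxiety and biomarker; (3) biomarker on anxiety. Use one pre-delivery anxiety summary per woman, since outcome and biomarker have one value each. Test the indirect effect directly, for example with a bootstrap interval, without requiring step 1 to be significant.

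In 9.3, state whether purpose 3 means mediation, effect modification or both, and align its wording with the models. To answer it as now worded, add an anxiety-by-biomarker term to model 2.

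Add a limitation: biomarkers sampled at delivery are concurrent with the birth outcome, so even the re-ordered model does not prove causal order.

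A secondary point: keep logistic models for preterm birth and low birth weight, and use linear models where gestational age or birth weight is analysed as continuous.

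The cost is rewording 11.6 and purpose 3, one limitation sentence, one interaction term and one interval. The data and the number of models stay the same.
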